3.2. General Methods

Formal statistical hypothesis testing will be performed on the primary efficacy endpoint conducted at the nominal 2-sided, 0.05 level of significance. All non-primary endpoint summaries will be descriptive.

All output will be incorporated into Microsoft Word files, sorted and labeled according to the International Conference on Harmonisation (ICH) recommendations, and formatted to the appropriate page size(s).

Continuous data will be described using descriptive statistics such as the number of observations (n), mean, standard deviation (SD), standard error of the mean (SEM), median, minimum, and maximum. For the summary statistics of all numerical variables, unless otherwise specified, minimum and maximum will be displayed to the same level of precision as reported. The mean, SD, SEM and median will be reported to one greater decimal place.

For laboratory data, if any value is recorded as less than the lower limit of quantification (LLOQ), then the value used for calculation will be assigned a value of LLOQ.

Categorical and ordinal data will be tabulated using the patient count and percentages in each category unless otherwise specified. When count data are presented, the percentage will not be presented when the count is zero. A percentage of 100% will be reported as 100% without any decimal places.

Study Day 1 will be defined as the day of the first dose of patisiran in this study. Study Day will be calculated relative to the first dose date of study drug for all patients:

If the assessment date is after the date of first study drug dose, then the study day will be calculated as:

$$\text{Study Day} = \text{Date of assessment} - \text{date of first dose of study drug} + 1,$$

If the assessment date is before the date of the first dose of study drug, then the study day will be calculated as:

$$\text{Study Day} = \text{Date of assessment} - \text{date of first dose of study drug}.$$

All data recorded on the eCRF will be included in data listings.

3.3. Computing Environment

All descriptive statistical analyses will be performed using SAS statistical software Version 9.4 (or later), unless otherwise noted. Medical history and AEs will be coded using the Medical Dictionary for Regulatory Activities (MedDRA) version 23.0 (or later). Premedications, prior

and concomitant medications will be coded using the World Health Organization (WHO) Drug Dictionary version September 2018 (or later).

3.4. Baseline Definitions

Unless noted otherwise, baseline will be defined as the last non-missing evaluable measurement on or prior to the first dose of patisiran in this study.

For TTR, baseline will be defined as the average of all records, including those from any unscheduled visits, prior to the date and time of first dose.

3.5. Adjustments for Covariates

The single hypothesis in this study will be tested using the Wilcoxon signed-rank test, a nonparametric test for paired data. Adjustment for covariates will not be performed for this analysis.

3.6. Multiple Comparisons/Multiplicity

Multiplicity is not of concern for this study with a single hypothesis to be tested.

3.7. Subpopulations

No analyses of patient subgroups are planned.

3.8. Withdrawals, Dropouts, and Loss to Follow-up

A patient may stop participation in the study-at any time and for any reason.

A patient considering stopping participation in the study should be informed that they can discontinue study drug and/or decline procedural assessments and remain in the study for the collection of important study data as described in the Protocol.

If a patient still chooses to discontinue study drug and stop participation in all follow-up, every effort should be made to conduct the end of study assessments within 4 weeks of the last dose.

When a patient discontinues study treatment and/or withdraws from the study, the primary reason for withdrawal must be recorded in the appropriate section of the eCRF, and all efforts will be made to complete and report the observations as thoroughly as possible.

A patient will be considered lost to follow-up if the patient repeatedly fails to return for scheduled visits and is unable to be contacted by the clinical study center.

3.9. Onset of Serious COVID-19 Adverse Events

Secondary and exploratory efficacy assessments on or after the onset of a serious COVID-19 AE for a patient may be censored. The sponsor will review the reported events and determine if the impacts on efficacy warrants censoring.

3.10. Missing Data

For efficacy endpoints, the number and percentage of patients with missing data, including due to the COVID-19 pandemic, at each scheduled visit will be summarized.

3.10.1. Handling of Missing Data for Secondary Endpoints

For NIS, Norfolk QoL-DN, R-ODS and mBMI efficacy assessments, the primary analysis will be based on the last observation carried forward (LOCF) method, which makes use of the patient's previous observed post-baseline assessment value to impute the missing post-baseline assessment. Specifically, for NIS, Norfolk QoL-DN, and R-ODS, a missing value for the assessment at Month 12 will be imputed using the patient's observed value at month 6; for mBMI, a missing value for a post-baseline assessment at or after month 6 will be imputed by using the patient's most recent observed post-baseline value.

Specific algorithms will be used to impute values and/or subcomponents of particular assessments when subcomponents are missing (NIS, Norfolk QoL-DN, R-ODS, and COMPASS-31; see Section 7.1.1, Section 7.1.2, Section 7.1.3, and Section 7.1.4, respectively). The result of the partial imputation (either a non-missing or missing value) will be used in all statistical analyses.

There will be no imputation for missing data for other efficacy endpoints unless otherwise specified. All data recorded on the eCRF will be included in data listings that will accompany the CSR.

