Concomitant Medications and Procedures	See Section 5.3	X			Continuous														
Liver Allograft Status	See Section 6.3.4	X						X			X		X		X		X		

Table 1: Schedule of Assessments

		Screening	Baseline ^a	Dosing							6-Month Efficacy	Dosing				12-Month Efficacy	Early Termination	Safety Follow Up	
				D-42 to -1	Pre-Dose Day 1	D1	W1-2	W3 ±3D	W6 & 9 ±3D	W12 ±3D		W15 to 21 ±3D	W24 ±3D	W25 to W26 ±3D	W27 to W33 ±3D				W36 ±3D
Study Day (±Visit Window)	Notes																		
Weight	See Section 6.1.4		X	X		X	X	X	X	X	X	X	X	X	X	X		X	
Premedication and Study Drug Administration	Phone contact for home infusions only			X		X	X	X	X	X		X	X	X	X				

Abbreviations: COMPASS=Composite Autonomic Symptom Score; DNA=deoxyribonucleic acid; ECG=electrocardiogram; FAP=familial amyloidotic polyneuropathy; HIV=human immunodeficiency virus; LFT=liver function test; M=month; mBMI=modified body mass index; NIS=neurological impairment scale; NYHA=New York Heart Association; NT-proBNP=N-terminal prohormone of B-type natriuretic peptide; PK=pharmacokinetic; PND=paroxysmal nocturnal dyspnea; QoL= quality of life; R-ODS=Rasch-built Overall Disability Scale; TTR=transthyretin; W=week.

Notes: The Screening visit must be performed within 42 days before the first dose of study drug (Day 1).

Early termination visit should occur within 7 days of the decision to stop participating in the study.

Table 2: Pharmacokinetic Time Points

Study Visit	Day 1	Week 1-2	Week 3	Week 24	Week 54	Week 55-56	Week 57
Pre-Dose	X		X	X	X		
End of Infusion	X			X	X		
4 ± 1 h post EOI	X				X		
24 ± 4 h post EOI	X				X		
72 ± 6 h post EOI	X				X		
Day 7 to Day 14 post EOI		X				X	
Day 21 post EOI							X

TABLE OF CONTENTS

PROTOCOL SYNOPSIS	4
TABLE OF CONTENTS.....	13
LIST OF TABLES	16
LIST OF FIGURES	16
LIST OF ABBREVIATIONS AND DEFINITIONS OF TERMS.....	17
1. INTRODUCTION.....	19
1.1. Disease Overview	19
1.2. Patisiran-LNP (ALN-TTR02).....	20
1.3. Study Design Rationale	20
1.4. Dose Rationale.....	21
1.5. Benefit-Risk Assessment.....	21
2. OBJECTIVES AND ENDPOINTS.....	23
3. INVESTIGATIONAL PLAN.....	23
3.1. Summary of Study Design.....	23
3.2. Duration of Treatment	24
3.3. Duration of Study Participants.....	24
3.4. Number of Planned Patients	24
3.5. Safety Review Committee	24
4. SELECTION AND WITHDRAWAL OF PATIENTS.....	24
4.1. Inclusion Criteria	24
4.2. Exclusion Criteria	25
4.3. Removal from Study Drug or Assessment	27
4.3.1. Discontinuation of Study Drug or Declining Procedural Assessments	27

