3.11. Visit Windows

It is expected that all visits should occur according to the protocol schedule. All data will be tabulated per the evaluation visit as recorded on the eCRF even if the assessment is outside of the visit window.

For efficacy endpoints other than serum TTR level and mBMI, if the scheduled Month 6 or Month 12 assessments are not performed, any evaluable assessment will be grouped with the Month 6 or Month 12 assessments if it is performed within 3 months of the scheduled assessment. For mBMI, if the scheduled Week 12, Month 6, Week 36 or Month 12 assessments for mBMI are not performed, any evaluable assessment will be grouped with the scheduled assessments if it is performed within 1.5 months of the scheduled assessment.

Unless otherwise specified above, data collected at unscheduled visits will be included in by-patient data listings and figures, but no assignment to a study visit will be made for by-visit summary tabulations. However, unscheduled visits will be considered for baseline values, as discussed in Section 3.4, and for inclusion in any categorical shift summaries (eg, shift from baseline to “worst” post-baseline value).

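### For patients who leave the study between Month 6 and about Week 42, the LOCF rule for NIS, Norfolk QoL-DN and R-ODS fills Month 12 with the Month 6 score even when a later Early Termination score exists

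*SAP*

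**What the plan says.** SAP Section 3.10.1 names last observation carried forward (LOCF) as the primary approach for NIS, Norfolk QoL-DN, R-ODS and mBMI, and describes it as a method "which makes use of the patient's previous observed post-baseline assessment value to impute the missing post-baseline assessment". It then applies the method in two ways. For NIS, Norfolk QoL-DN and R-ODS the rule reads: "a missing value for the assessment at Month 12 will be imputed using the patient's observed value at month 6". The mBMI rule differs: a missing value at or after Month 6 is "imputed by using the patient's most recent observed post-baseline value".

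SAP Section 3.11 decides when an off-schedule score may stand in for a visit. For these three scales, "if the scheduled Month 6 or Month 12 assessments are not performed", then "any evaluable assessment will be grouped with the Month 6 or Month 12 assessments if it is performed within 3 months of the scheduled assessment". The same section begins with a general rule: "All data will be tabulated per the evaluation visit as recorded on the eCRF even if the assessment is outside of the visit window".

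Protocol Table 1 has an Early Termination column, and the NIS, Norfolk and R-ODS rows each carry four marks. The columns are shifted in the extracted table; I read the marks as Baseline, Month 6, Month 12 and ET. The table notes add: "Early termination visit should occur within 7 days of the decision to stop participating in the study".

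SAP Section 5 justifies LOCF for these three scales by the stability of their changes between Months 9 and 18 in the patisiran arm of the earlier placebo-controlled study.

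**The concern.** LOCF is meant to use the last thing known about the patient. Here, a patient who attends Month 6, leaves some weeks later and is examined at ET has a later score on file, yet the rule reaches back past it. Whatever happened between Month 6 and withdrawal, worsening included, is then absent from the Month 12 change, which is the secondary endpoint. Entry required documented progression, so change late in follow-up is of direct interest. With about 20 patients, one substituted score can be visible in a mean.

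The choice also sits badly with the SAP's own text. It departs from the general LOCF description in the same section and from the mBMI rule beside it. The stability argument in Section 5 starts at Month 9, so it does not cover a carry-forward that starts at Month 6.

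**Working it through.** **The plan's own figures.** Half-width = t(0.975, 15) × 18/√16 = 9.59 (8.82 with the normal quantile), which agrees with the stated value of about 10%. Enrolment = 16/(1 − 0.20) = 20. Both reproduce. Only the discontinuation rate is used below: 0.20 × 20 = 4 patients.

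**Inputs.** The efficacy visits are at Weeks 25–26 and 55–56 (Protocol Table 1; Protocol Administrative Change 1). The window is 3 months = 91 days = 13 weeks (SAP 3.11).

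**Windows.**
- Month 6 closes at 25 + 13 = Week 38 to 26 + 13 = Week 39.
- Month 12 opens at 55 − 13 = Week 42 to 56 − 13 = Week 43.
- Sensitivity: if Month 12 were anchored at Week 54 or Week 52, its window would open at Week 41 or Week 39.

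**What happens to an ET score.**

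| Month 6 done? | ET date | Use of the ET score for Month 12 |
|---|---|---|
| Yes | about W27–W42 | Not used. The Month 6 slot is filled and Month 12 is out of reach, so Month 6 is carried forward |
| No | within the Month 6 window, up to about W38–39 | Becomes the Month 6 value and is carried forward |
| No | about W39–W42 | Falls in neither window, with no Month 6 value to carry; Month 12 stays missing |
| Either | about W42–43 or later | Grouped with Month 12 and used |

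In the first row the carried score is older than the ET score by up to 42 − 26 = 16 weeks, or 43 − 25 = 18 weeks at the widest reading.

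**Number affected.** Assume that all 4 discontinuers leave the study, that they do so evenly over 56 weeks, that they attend ET, and that they had a Month 6 assessment.
- W27–W42: 4 × 15/56 = 1.1 patients.
- Widest reading, W26–W43: 4 × 17/56 = 1.2.
- Month 12 anchored at Week 52, W27–W39: 4 × 12/56 = 0.9.
- Possible range: 0 to 4.

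**Effect on a mean.** If one patient's NIS changed by d points between Month 6 and ET, the Month 12 mean over 16 to 20 patients moves by d/20 to d/16. The documents give no value for d. Assumed values: d = 5 gives 0.25 to 0.31; d = 10 gives 0.5 to 0.63; d = 20 gives 1.0 to 1.25. The NIS runs from 0 to 244.

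**Reach of the stability rationale.** Month 9 is 9 × 30.4375/7 = Week 39. The Month 6 score at Weeks 25–26 lies before the period that the rationale describes. An ET score at about Weeks 39–42 lies inside it. An ET score before Week 39 also lies outside, but closer.

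**The case against.** The best defence is that the two LOCF rules reflect two schedules. NIS, Norfolk QoL-DN and R-ODS have only Month 6 and Month 12 as scheduled on-study post-baseline visits, so the previous scheduled value before Month 12 is Month 6. SAP 3.11 lists four mBMI time points (Week 12, Month 6, Week 36, Month 12), so that scale needs a most-recent rule. This probably explains the wording, and it means that the two LOCF sentences need not be read as irreconcilable. It does not answer the point, because ET is also a scheduled assessment of these scales and the specific rule passes over it.

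Three stronger readings are tempting and are not supported.
- A reader might infer that ET scores are thrown away. They are not. SAP 3.10.1, 4.4.2.1 and 4.4.2.2 keep observed scores in listings, and the opening rule of 3.11 allows tabulation under the visit recorded on the eCRF. The sentence in 3.11 that withholds visit assignment concerns unscheduled visits, and ET is a named visit.
- A reader might infer that everyone who stops between about Week 27 and Week 42 is affected. What counts is a completed Month 6 assessment and the date of the ET assessment, not the date of stopping. ET may follow the decision by up to 7 days, and SAP 3.8 asks for end-of-study assessments within 4 weeks of the last dose, so some who stop shortly before Week 42 fall inside the Month 12 window. Protocol Section 4.3.1 encourages patients who stop only the drug to stay through Month 12; those who do are unaffected.
- A reader might infer a bias toward stability or benefit. The documents do not say why patients would leave, and a patient who improved after Month 6 would shift the mean the other way.

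It also stands that SAP 3.2 makes all non-primary summaries descriptive. No test, sample size or TTR result depends on this rule.

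**Conclusion.** The point holds in a narrow form. When Month 6 was assessed and the ET assessment falls more than 3 months before the scheduled Month 12 visit, the SAP replaces a later measured score with an older one. When Month 6 was not assessed and ET falls between about Week 39 and Week 42, a measured score exists but Month 12 stays empty. This is a stated rule with a better alternative at hand, not a missing detail.

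The expected size is about 1 patient, and it rests on the four assumptions in the working: discontinuation means leaving the study, timing is even, ET is attended and Month 6 was done. The first of these pushes the estimate upward. The direction of the effect cannot be known in advance; what is certain is that change after Month 6 is hidden for these patients. The change is worth making because it is cheap and the study is small, but the consequence is confined to descriptive secondary summaries.

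**What to change.** In SAP 3.10.1, state that for NIS, Norfolk QoL-DN and R-ODS a Month 12 value still missing after the Section 3.11 windows are applied is imputed with the patient's most recent evaluable post-baseline value, including ET, and that the Month 6 value is used only if nothing later exists. Add a cross-reference in 3.11 so that ET scores falling between the windows are handled in the same way, and say under which visit they are tabulated.

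The cost is a short text change in two sections and a small programming change; no new data are needed. The Month 12 change may look slightly less favourable if the patients concerned were worsening. As worded, the rule would also carry forward an ET score from before the Month 6 window (before about 25 − 13 = Week 12) when nothing later exists, so the sponsor should say whether that is intended. If the SAP is already final, Protocol Section 7.2 provides for describing and justifying the change in the clinical study report.

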3.10.2. Other Missing Data

For records with fully or partially missing AE onset date and/or stop date, conventions for determining whether an AE is treatment emergent and calculating start/end study day of an AE is as below:

- AE onset dates with missing day and non-missing month will be assumed to occur on the first day of the non-missing month, except for AEs occurring in the first month of dosing, in which case the date will be the first day of dosing.
- AE onset dates with missing month will be assumed to occur on the first day of the non-missing year (ie, January 1), except for AEs occurring in the first year of dosing, in which case the date will be the first day of dosing.
- If year of the AE start date is missing, no date imputation will be made, but the AE will be considered treatment-emergent.
- An AE that is not ongoing and has a stop date with a missing day and non-missing month will be assumed to occur on the last day of the non-missing month.
- An AE that is not ongoing and has a stop date with a missing month will be assumed to occur on the last day of the non-missing year (ie, December 31).

For the calculation of duration (eg, time in years since diagnosis with hATTR) in the presence of an incomplete date, the following conventions will be used:

- Missing day: the first day of the month will be used;
- Missing month: duration will be calculated as the simple difference in years (eg, year of informed consent minus year of diagnosis with hATTR);
- Missing year: no duration will be calculated.

3.11. Visit Windows

It is expected that all visits should occur according to the protocol schedule. All data will be tabulated per the evaluation visit as recorded on the eCRF even if the assessment is outside of the visit window.

For efficacy endpoints other than serum TTR level and mBMI, if the scheduled Month 6 or Month 12 assessments are not performed, any evaluable assessment will be grouped with the Month 6 or Month 12 assessments if it is performed within 3 months of the scheduled assessment. For mBMI, if the scheduled Week 12, Month 6, Week 36 or Month 12 assessments for mBMI are not performed, any evaluable assessment will be grouped with the scheduled assessments if it is performed within 1.5 months of the scheduled assessment.

Unless otherwise specified above, data collected at unscheduled visits will be included in by-patient data listings and figures, but no assignment to a study visit will be made for by-visit summary tabulations. However, unscheduled visits will be considered for baseline values, as discussed in Section 3.4, and for inclusion in any categorical shift summaries (eg, shift from baseline to “worst” post-baseline value).

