7.1.3. Rasch-Built Overall Disability Scale (R-ODS)

The R-ODS consists of 24 items scored on a scale of 0 (unable to perform), 1 (able to perform, but with difficulty) or 2 (able to perform without difficulty). A total score will be calculated as the average of all non-missing items multiplied by 24 if at least 90% of the items are non-missing. The total score will be deemed as missing if more than 10% of the items (3 or more items) are missing.

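### SAP 3.11 accepts a substitute Month 6 or Month 12 assessment only when the scheduled one was not performed, so one that was performed but cannot be scored shuts out a complete unscheduled repeat

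*SAP*

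**What the plan says.** SAP 3.11 sets three rules that matter here.

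- **Visit label.** "All data will be tabulated per the evaluation visit as recorded on the eCRF even if the assessment is outside of the visit window".
- **Substitution.** For efficacy endpoints other than serum TTR and mBMI, "if the scheduled Month 6 or Month 12 assessments are not performed, any evaluable assessment will be grouped" with Month 6 or Month 12 "if it is performed within 3 months of the scheduled assessment".
- **Default.** For other data from unscheduled visits, "no assignment to a study visit will be made for by-visit summary tabulations"; such data go to listings and figures. Baseline values and categorical shift summaries are excepted.

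SAP 7.1.1 to 7.1.4 define when an administered instrument has no total. For R-ODS, for example, "The total score will be deemed as missing if more than 10% of the items (3 or more items) are missing".

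SAP 3.10.1 makes the scoring outcome binding: "The result of the partial imputation (either a non-missing or missing value) will be used in all statistical analyses". For NIS, Norfolk QoL-DN and R-ODS it adds that "a missing value for the assessment at Month 12 will be imputed using the patient's observed value at month 6". COMPASS-31 has no LOCF; SAP 4.4.2.3 analyses it with an MMRM.

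The baseline rule in SAP 3.4 is worded differently: "baseline will be defined as the last non-missing evaluable measurement on or prior to the first dose of patisiran".

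**The concern.** In the substitution rule, the requirement to be evaluable applies to the replacement and not to the assessment being replaced. A form that was handed in but cannot be scored counts as performed, so the trigger is not met. If the site then obtains a complete repeat and records it as unscheduled, the repeat is listed but left out of the by-visit summaries.

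Two patients with the same good repeat are therefore handled differently. The one who skipped the scheduled assessment keeps the repeat, and the one who left too many items blank loses it. Nothing in the SAP explains the difference, and the baseline rule shows that the plan elsewhere selects on evaluability.

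At stake is an observed score near Month 12 giving way to one about seven months older. The SAP's reason for LOCF (Section 5) is that NIS, Norfolk QoL-DN and R-ODS were relatively stable between Months 9 and 18 in the patisiran arm of the pivotal Phase 3 study. That interval does not include the start of the step used here, from Month 6 to Month 12.

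**Working it through.** **1. Can a performed assessment lack a total?** The plan's own thresholds reproduce.

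| Instrument | Rule (SAP 7.1) | Arithmetic |
|---|---|---|
| R-ODS | missing if more than 10% of 24 items are blank | 0.10 × 24 = 2.4, so 3 or more blank; at least 22 answered (0.90 × 24 = 21.6) |
| Norfolk QoL-DN | missing if a domain is missing and under half of 35 items are answered | 0.50 × 35 = 17.5, so 18 items are needed |
| NIS | total missing if any of three components is missing | side-specific items 48 + 10 + 16 = 74; maxima 48 × 4 = 192, 10 × 2 = 20, 16 × 2 = 32 |
| COMPASS-31 | missing if more than 2 of 6 domains are missing | 3 or more domains |

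So all four can be performed and unscorable.

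**2. What happens next at Month 12?**

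| | Scheduled assessment skipped | Performed, no total |
|---|---|---|
| Substitution trigger (3.11) | met | not met |
| Complete unscheduled repeat within 3 months | grouped with Month 12 | no visit assignment |
| NIS, Norfolk QoL-DN, R-ODS at Month 12 | repeat score | Month 6 score if observed, otherwise missing |
| COMPASS-31 at Month 12 | repeat score | missing in the MMRM |

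The trigger works the same way at Month 6. SAP 3.10.1 specifies no imputation there for NIS, Norfolk QoL-DN or R-ODS, so the Month 6 value stays missing.

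**3. How old is the carried score?** Protocol Table 1 and Administrative Change 1 put the efficacy visits at Weeks 25 to 26 and Weeks 55 to 56. The gap is 55 − 26 = 29 to 56 − 25 = 31 weeks.

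**4. Effect on the mean.** Let D be a patient's change from Month 6 to Month 12, with the repeat taken as the Month 12 value. Using the Month 6 score instead moves the group mean by D/n in size. Baseline is the same either way, so the mean change from baseline moves equally. For n, SAP 3.1 gives 16 evaluable and 16/(1 − 0.20) = 20 enrolled.

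- One affected patient: 1/20 = 5% to 1/16 = 6.25% of D.
- Two, each with change D: 2/20 = 10% to 2/16 = 12.5% of D.
- Three, each with change D: 3/20 = 15% to 3/16 = 18.75% of D.

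The Per Protocol Analysis Set, used for these endpoints, could be smaller than 16, and the weight would then rise as 1/n. The formula does not apply to COMPASS-31, where the MMRM uses the patient's other data under missing at random.

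**The case against.** The strongest reply is that the route is narrow. It needs a performed but unscorable assessment, a complete repeat that the protocol does not schedule (efficacy is assessed at baseline, Month 6 and Month 12), and an unscheduled label on the eCRF. For carry-forward it also needs a scorable Month 6 value. Norfolk QoL-DN and COMPASS-31 tolerate a good deal of missingness before the total is lost. The repeat stays in the listings, SAP 3.10 tabulates missing efficacy data by visit, and all non-primary summaries are descriptive. A programmer might also read 'not performed' as 'no evaluable result'. All of this stands as a limit on size and frequency. It does not remove the gap, because the term is undefined and the literal text points the other way.

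A reader might infer more than the documents support:

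- *That every repeat is blocked.* A repeat entered under the Month 12 eCRF visit is tabulated as Month 12. The SAP gives no rule for choosing between two such records, but that is a separate question.
- *That all questionnaires are carried forward.* COMPASS-31 is not. With one or two domains missing, its total is completed from other patients' domain averages and is not missing at all.
- *That KPS, PND, FAP and mBMI are affected.* The first three are single ratings with no Section 7.1 scoring, and shift tables already admit unscheduled data. The documents show no way for an mBMI to be performed but unscorable.
- *That later worsening is hidden by a known number of points.* The documents give neither D nor a rate of unscorable assessments.

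**Conclusion.** The point holds in a limited form. On the literal text of SAP 3.11, an unscorable NIS, Norfolk QoL-DN, R-ODS or COMPASS-31 excludes a complete repeat recorded as unscheduled, whereas a skipped assessment does not. For the first three, the Month 12 mean then moves by 5% to 6.25% of D per affected patient, given n of 20 to 16, a scorable Month 6 value, and a repeat that represents Month 12. For COMPASS-31 an observed value is lost to the model.

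Severity is low. The primary TTR endpoint is outside this rule, the affected endpoints are descriptive, and the case is probably rare, though the documents give no frequency. If scores are in fact stable from Month 6 to Month 12, D is small and so is the shift. The change is worth making because the present trigger has no stated reason and the better rule uses only data already collected.

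**What to change.** In SAP 3.11, for NIS, Norfolk QoL-DN, R-ODS and COMPASS-31:

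1. Replace 'are not performed' with 'are not performed or do not give an evaluable total score under Section 7.1'.
2. Use the evaluable assessment closest to the scheduled date within the existing 3-month window.
3. In SAP 3.10.1, apply LOCF to NIS, Norfolk QoL-DN and R-ODS only if no such assessment exists.

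Leave the wording for KPS, PND, FAP and mBMI as it is. Section 7.1 does not score them, so the new phrase would point to nothing.

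The cost is one phrase, one selection rule and a small change to the derivation code. No new data are collected and the window does not widen. The derivation should also state whether component and domain scores are taken from the same substitute assessment as the total.
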